## **Appendix 5. KARNOFSKY PERFORMANCE STATUS SCALE DEFINITIONS RATING (%) CRITERIA**

### **KARNOFSKY PERFORMANCE STATUS SCALE DEFINITIONS RATING (%) CRITERIA**

Able to carry on normal activity and to work; no special care needed.	100	Normal no complaints; no evidence of disease.
	90	Able to carry on normal activity; minor signs or symptoms of disease.
	80	Normal activity with effort; some signs or symptoms of disease.
Unable to work; able to live at home and care for most personal needs; varying amount of assistance needed.	70	Cares for self; unable to carry on normal activity or do active work.
	60	Requires occasional assistance, but is able to care for most of his personal needs.
	50	Requires considerable assistance and frequent medical care.
Unable to care for self; requires equivalent of institutional or hospital care; disease may be progressing rapidly.	40	Disabled; requires special care and assistance.
	30	Severely disabled; hospital admission is indicated although death not imminent.
	20	Very sick; hospital admission necessary; active supportive treatment necessary.
	10	Moribund: fatal processes progressing rapidly
	0	Dead

Reference:

[http://www.npcrc.org/usr\\_doc/adhoc/functionalstatus/Karnofsky%20Performance%20Scale.pdf](http://www.npcrc.org/usr_doc/adhoc/functionalstatus/Karnofsky%20Performance%20Scale.pdf)

## Appendix 6. Revised Schedule of Activities Following Collection of Data for Primary Study Objective

After the collection of data for the primary study objective and most of the secondary objectives has been completed, patients who are still clinically benefiting from study treatment as judged by the investigator may be candidates for continuation of study treatment. Discussion with sponsor is required.

The following protocol sections should be disregarded: [Schedule of Activities](#) the original protocol and the trial procedures in [Section 6.2](#) Study Period, [7.2](#) Pharmacokinetics Assessments, [7.2.1](#) Blood Sample Collection for Pharmacokinetic Analysis, [7.2.2](#) Collection of Axitinib PK Samples, [7.2.3](#) Processing, Storage and Shipment of Axitinib PK Samples, [7.2.4](#) Collection and Processing of MK-3475 PK Samples, [7.2.5](#) Collection and processing of anti-MK3475 Antibody Samples, and [7.3](#) Translational and Pharmacodynamic Assessments. The investigator may schedule visits (unplanned visits) in addition to those listed in the [Schedule of Activities](#) table in order to conduct evaluations or assessments required to protect the well-being of the patient.

The following schedule of activities will be implemented for patients still on active treatment and long-term survival follow-up. Patients on axitinib monotherapy have the opportunity to continue axitinib treatment on a Pfizer-sponsored patient access program at the time of the discontinuation of survival status follow-up.

Protocol Activities and Forms to be Completed	Study Treatment 	Post-Treatment		
	Cycles ≥24 Day 1 -3/+3	End of Tx or Withdrawal  -3/+3	28 Days Post-Treatment -7/+7	Survival Follow-Up -7/+7
Physical Examination 	X	X		
In Clinic Blood Pressure, Pulse Rate 	X	X		
Home Blood Pressure Monitoring 	X	X		
Hematology 	Local Standard of Care	X		
Blood Chemistry 	Local Standard of Care	X		
Coagulation 	Local Standard of Care			
Urinalysis 	X			
12-lead ECG 	X	X		
Thyroid Function Tests 	X	X		
Pregnancy Test 	X	X		
Tumor Assessments 	Local Standard of Care and at End of Treatment			
Adverse Events 	X	X	X	
Concomitant Medications/Treatments 	X	X	X	
Study Treatment 	X			
Post Study Survival Status 			X	X

Footnotes for Schedule of Activities
1. During Treatment: All assessments should be performed prior to dosing with study treatment unless otherwise indicated. Acceptable time windows for performing each assessment are described in the column headings.  Patients who permanently discontinue pembrolizumab and continue on axitinib treatment, it is at the discretion of the investigator to follow patients on axitinib monotherapy every 3 weeks + or – 3 days (ie, cycle=21 days) or 6 weeks + or – 3 days (ie, cycle=42 days). All tests and assessments outlined in the schedule of activities must be conducted at that visit.
2. End of Study Treatment/Withdrawal: Obtain these assessments if not completed during the previous two weeks on study.
3. Physical Examination: Includes an examination of major body systems and weight.
4. In Clinic Blood pressure, pulse rate: Blood pressure, and pulse rate should be taken with the patient in the seated position after the patient has been sitting quietly for at least 5 minutes. Two blood pressure readings will be taken at least 1 hour apart at each clinic visit.
5. Home blood pressure monitoring: All patients will receive home blood pressure monitoring devices and blood pressure will be monitored at home. While on axitinib (as single agent or combined with MK 3475) patients will monitor their blood pressure at least twice daily (before taking each dose of axitinib) and blood pressure should be recorded in a patient diary. Patients should be instructed to contact the site immediately for guidance if their systolic blood pressure rises above 150 mm Hg, diastolic blood pressure rises above 100 mm Hg, or if they develop symptoms perceived to be related to elevated blood pressure (eg, headache, visual disturbance) although a different blood pressure threshold for contacting the site may be used according to the Investigator's clinical judgment (see Section 5.2.7.3 ).
6. Hematology, Blood Chemistry, and Coagulation: Required tests are listed in Table 8 . All laboratory tests may be performed per standard of care and when clinically indicated. Dose adjustment may be required (see Section 5.2.7 ).
7. If protein $\geq 2+$ by semiquantitative method (eg, urine dipstick), protein will have to be quantified by 24 hour urine collection. Dose adjustment may be required (see Section 5.2.7.2 ). May be performed also when clinically indicated.
8. Single ECG measurement will be obtained at End of Treatment/Withdrawal. Additionally, ECGs should be performed when clinically indicated. Clinically significant findings seen on follow-up ECGs should be recorded as adverse events.
9. Subsequently, TSH should be assessed every 6 weeks thereafter starting from Cycle 24 Day 1. Free T3 and free T4 should additionally be performed when clinically indicated. Hypothyroidism should be treated per standard medical practice to maintain euthyroid state. See Table 8 .
10. For female patients of childbearing potential, a serum or urine pregnancy test, with sensitivity of at least 25 mIU/mL, will be performed and routinely repeated at every cycle during the active treatment period, at the end of study treatment and additionally whenever one menstrual cycle is missed or when potential pregnancy is otherwise suspected. Pregnancy tests may also be repeated as per request of IRB/IECs or if required by local regulations (see Section 7.1.1 ).
11. Tumor assessments will include all known or suspected disease sites: frequency to be performed per local standard of care and again at treatment withdrawal if not performed within previous 6 weeks. Tumor imaging must be measured using RECIST version 1.1 tumor assessment criteria to determine disease progression.
12. Adverse Events: Adverse events should be documented and recorded at each visit using NCI CTCAE version 4.03. For SAEs, the active reporting period to Pfizer or its designated representative begins from the time that the patient provides informed consent, which is obtained prior to the patient's participation in the study, ie, prior to undergoing any study related procedure and/or receiving investigational product, through and including 90 calendar days after the last administration of the investigational product and before initiation of a new anti-cancer treatment. The prolonged follow up is due to the pharmacokinetic properties of the investigational product MK-3475. SAEs experienced by a patient after the active reporting period (see Section 8.1.4 ) has ended should be reported to the Sponsor if the Investigator becomes aware of them; at a minimum, all SAEs that the Investigator believes have at least a reasonable possibility of being related to study drug are to be reported to the Sponsor. AEs (serious and non serious) should be recorded on the Case Report Form (CRF) from the time the patient has taken at least one dose of study treatment through last patient visit (Day 28 after last dose). If a patient begins a new anticancer therapy, the AE reporting period for non serious AEs ends at the time the new treatment is started. Pregnancy or breast feeding that occur during the trial, within 120 days of discontinuing treatment with MK-3475, or within 28 days after the cessation of axitinib if the patient begins a new anticancer therapy, whichever is earlier, should be reported as in Section 8.4.2.1 (Exposure During

Pregnancy).
13. Concomitant medications and treatments will be recorded from 28 days prior to the start of study treatment and up to 28 days after the last dose of study treatment. All concomitant medications should be recorded in the CRF including supportive care drugs (eg, anti emetic treatment and prophylaxis), and the drugs used to treat adverse events or chronic diseases, and non-drug supportive interventions (eg, transfusions).
14. Study treatment: will be administered as in Section 5.2.4.2.1 Axitinib will be given orally twice daily PO on a continuous schedule. MK-3475 will be given as a 30 minute intravenous infusion every 3 weeks. (one Cycle = 3 weeks) (see Section 5 ). Patients with disease progression who are continuing to derive clinical benefits from the study treatment may continue treatment with axitinib provided that the treating physician has determined that the benefit/risk for doing so is favorable and after discussion with the sponsor. Continuation of treatment with MK-3475 beyond 24 months should be discussed with the sponsor and not go beyond 36 months. Patients who permanently discontinue pembrolizumab and continue on axitinib treatment, it is at the discretion of the investigator to follow the patient on axitinib monotherapy every 3 weeks + or - 3 days (ie, cycle=21 days) or 6 weeks + or- 3 days (ie, cycle=42 days). All tests and assessments outlined in Appendix 6 Schedule of Activities must be conducted at that visit or when clinically indicated. Patients on axitinib monotherapy have the opportunity to continue axitinib treatment on a Pfizer-sponsored program at the time of the discontinuation of survival status follow-up.
15. Survival: All patients should be followed for survival at least every 3 months after discontinuing study treatment. Survival monitoring will continue until approximately 3 years after last patient has been enrolled. Information on antineoplastic treatments (ie, systemic, surgery, and radiotherapy) will be collected.

1. AMENDMENTS FROM PREVIOUS VERSION(S)

- Specifies analyses of safety data (adverse events and laboratory tests) which includes the period from the start of treatment with the axitinib + MK-3475 combination (CD1).
- Clarified language regarding analysis sets for efficacy endpoints. Clarified that data from patients treated at the MTD in the dose escalation and dose expansion portions of the study will be pooled for the secondary safety and efficacy analyses.
- Removed supportive efficacy analysis.

2. INTRODUCTION

This document describes the planned statistical analyses for Protocol A4061079. This analysis plan is meant to supplement the study protocol. In this document, any text taken directly from the protocol is *italicized*.

Any deviations from this main analysis plan will be described in the Clinical Study Report.

2.1. Study Design

This is a Phase 1b, open-label, multi-center, multiple-dose, safety, pharmacokinetics (PK) and pharmacodynamic study of axitinib in combination with MK-3475 in adult patients with previously untreated advanced renal cell carcinoma (aRCC). This clinical study will be composed of a Dose Finding Phase and a Dose Expansion Phase. The Dose Finding Phase will estimate the maximum tolerated dose (MTD) in patients with aRCC with clear cell histology who did not receive prior systemic therapy for the advanced disease, using the modified toxicity probability interval (mTPI) method.

The Dose Finding Phase will lead to the identification of an Expansion Test Dose for axitinib in combination with MK-3475 in patients with aRCC who did not receive prior systemic therapy. The Expansion Test Dose will be either the MTD (ie, the highest dose of axitinib and MK-3475 associated with the occurrence of dose limiting toxicities (DLTs) in <33% of patients) or the recommended phase II Dose (RP2D), ie, the highest tested dose that is declared safe and tolerable by the Investigators and Sponsor. Once the Expansion Test Dose is identified, the Dose Expansion Phase will be opened and axitinib in combination with MK-3475 will be tested in patients with previously untreated aRCC.

Anti-tumor activity will be assessed by radiological tumor assessments conducted at baseline, 12 weeks, and every 6 weeks thereafter, using response evaluation criteria in solid tumors (RECIST) version 1.1. In addition, radiological tumor assessments will also be conducted whenever disease progression is suspected (e.g., symptomatic deterioration), and at the time of End of Treatment/Withdrawal (if not done in the previous 6 weeks). Brain CT or MRI scans are required at baseline and when there is a suspected brain metastasis. Bone scan (bone scintigraphy) or ¹⁸F-FDG-PET/CT is required at baseline then every 15 weeks only if bone metastases are present at baseline. Otherwise bone imaging is required only if

new bone metastases are suspected. Bone imaging is also required at the time of confirmation of response for patients who have bone metastases.

MK-3475 and axitinib do not have competing elimination/metabolism pathways, hence an overt PK interaction between the two drugs is not anticipated. However, pharmacokinetic assessments will be conducted in this study to confirm the absence of drug-drug interactions. To understand the PK effects of MK-3475 on axitinib, a 7-day lead-in period with single-agent axitinib will be included prior to Cycle 1 in all patients in the Dose Finding Phase and in at least 8 patients in the Dose Expansion Phases of the study. On the contrary, the administration of single agent MK-3475 to this patient population is not considered in this trial. The effect of axitinib on MK-3475 will be evaluated by comparing MK-3475 trough concentrations at steady-state in the presence of axitinib with those reported for MK-3475 alone in prior studies. MK-3475 has a long half-life (21-28 days) and an increase in trough concentration over time is expected.

Archived tumor biospecimens, and baseline de novo biospecimens from metastatic lesions will be collected for all patients in the dose expansion cohort. Every effort will be made to obtain a second biopsy at the time of first tumor assessment at 12 weeks. Biomarker studies on tumor and blood biospecimens will be carried out to help understand the mechanism of action of the axitinib plus MK-3475 combination, as well as potential mechanisms of resistance. Such results may help in the future development of this combination. Analyses using translational approaches may also result in the identification of potential biomarkers of response to the axitinib plus MK-3475 combination, ultimately leading to the development of a patient selection strategy for further clinical investigation. As such, collection of tumor and blood biospecimens at baseline and on study will be of paramount importance.

2.2. Study Objectives

2.2.1. Primary Objective

- To assess the safety and tolerability of axitinib in combination with MK-3475 in patients with previously untreated advanced RCC in order to estimate the MTD and select the RP2D.*

2.2.2. Secondary Objectives

- To evaluate the overall safety profile of axitinib in combination with MK-3475.*
- To assess the anti-tumor activity of axitinib in combination with MK-3475 in patients with advanced RCC in the first-line treatment setting.*
- To characterize the PK of axitinib and axitinib plus MK-3475 when administered in combination, and to assess the effect of MK-3475 on the PK of axitinib.*
- To characterize, using translational approaches, genes and proteins such as PD-L1, VEGF-A and IL-8 relevant to angiogenesis drug target pathway, renal cell carcinoma biology, and sensitivity/resistance mechanisms to axitinib in combination with MK-3475 in tumor and/or blood.*

- *To explore the pharmacodynamic effect of axitinib in combination with MK-3475 in blood and tumor by assessment of gene, RNAs and proteins including but not limited to VEGF-A, IL-8 and VEGFR2 and T-cell receptors.*
- *To assess the immunogenicity of MK-3475.*

3. INTERIM ANALYSES, FINAL ANALYSES, AND UNBLINDING

This is an open label, single-arm trial for which no formal interim analysis is planned. The final analysis of efficacy will be performed approximately 18 months after enrollment of the last subject; however, earlier analyses of the data may be performed for publication and regulatory reporting purposes.

4. HYPOTHESES AND DECISION RULES

4.1. Statistical Hypotheses

The emphasis of the final analyses will be on estimation of key summary statistics rather than hypothesis testing.

4.2. Statistical Decision Rules

Up-and-Down Matrix Design with the mTPI Method

The dose escalation/de-escalation rules will follow the mTPI method (see Section 8 for a detailed description). Briefly, the mTPI method relies upon a statistical probability algorithm, calculated using data from all patients treated at the same dose level (and not simply those in the current cohort) to determine whether future cohorts should involve dose escalation, no change in dose, or dose de-escalation.

Maximum Tolerated Dose Definition

The MTD estimate is the highest dose of axitinib and MK-3475 associated with the occurrence of DLTs in <33% of patients.

Dose Expansion Phase Cohorts

Once the MTD (or the RP2D) for the combination has been defined, up to 40 response-evaluable patients with advanced RCC will be enrolled and treated in the Expansion Phase. The expansion phase will confirm the safety and tolerability as well as explore the antitumor activity of axitinib in combination with MK-3475 in patients with previously untreated advanced RCC.

5. ANALYSIS POPULATIONS

5.1. Safety Analysis Set

The safety analysis set includes all enrolled patients who receive at least one dose of axitinib or MK-3475. This is the primary population for all standard analyses.

5.2. Per Protocol Analysis Set (Evaluable for DLT)

All enrolled patients who are eligible, receive at least one dose of axitinib and MK-3475, and who either experience DLT during the first two cycles, or complete the observation period for the first two cycles of treatment (6 weeks). Patients who withdraw from study treatment before receiving at least 75% of the planned first two cycles doses of axitinib or two infusions of MK-3475 within the DLT observation period due to reasons other than treatment related adverse events are not evaluable for DLT.

5.3. Response Evaluable Analysis Set

All patients who receive study treatment (at least one dose of axitinib and MK-3475) with an adequate baseline tumor assessment will be considered evaluable for anti-tumor efficacy using standard RECIST 1.1 criteria.

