19. **Adverse Events:** Adverse events should be documented and recorded at each visit using NCI CTCAE version 4.03. For SAEs, the active reporting period to Pfizer or its designated representative begins from the time that the patient provides informed consent, which is obtained prior to the patient's participation in the study, ie, prior to undergoing any study-related procedure and/or receiving investigational product, through and including 90 calendar days after the last administration of the investigational product and before initiation of a new anti-cancer treatment. The prolonged follow up is due to the pharmacokinetic properties of the investigational product MK-3475. SAEs experienced by a patient after the active reporting period (see [Section 8.1.1](#)) has ended should be reported to the Sponsor if the Investigator becomes aware of them; at a minimum, all SAEs that the Investigator believes have at least a reasonable possibility of being related to study drug are to be reported to the Sponsor. AEs (serious and non serious) should be recorded on the Case Report Form (CRF) from the time the patient has taken at least one dose of study treatment through last patient visit (Day 28 after last dose). If a patient begins a new anticancer therapy, the AE reporting period for non serious AEs ends at the time the new treatment is started. Pregnancy or breast feeding that occur during the trial, within 120 days of discontinuing treatment with MK-3475, or within 28 days after the cessation of study treatment if the patient begins a new anticancer therapy, whichever is earlier, should be reported as in [Section 8.4 \(Exposure During Pregnancy\)](#).

20. **Concomitant Medications/Treatments:** Concomitant medications and treatments will be recorded from 28 days prior to the start of study treatment and up to 28 days after the last dose of study treatment. All concomitant medications should be recorded in the CRF including supportive care drugs (eg, anti-emetic treatment and prophylaxis), and the drugs used to treat adverse events or chronic diseases, and non-drug supportive interventions (eg, transfusions).

21. **Registration:** Patient number and dose level allocation operated by Pfizer Inc. Required information: site and patient identifiers and demographic information. Study treatment (either single agent axitinib for patients in Lead-in or axitinib in combination with MK-3475 for all other patients) should begin within 7 days of registration.

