### **9.1. Analysis Sets**

The following patient sets will be assessed.

- Safety analysis set.

The safety analysis set includes all enrolled patients who receive at least one dose of axitinib or MK-3475.

- Per protocol analysis set (evaluable for DLT).

All enrolled patients who are eligible, receive at least one dose of axitinib and MK-3475, and who either experience DLT during the first two cycles, or complete the observation period for the first two cycles of treatment (6 weeks). Patients who withdraw from study treatment before receiving at least 75% of the planned first two cycles doses of axitinib or two infusions of MK-3475 within the DLT observation period due to reasons other than treatment related adverse events are not evaluable for DLT. A patient who is unable to start at the assigned Cycle 1 Day 1 dose level after the lead-in period will not be evaluable for DLTs but will be evaluated for safety and efficacy.

- Response evaluable analysis set.

All patients who receive study treatment with an adequate baseline tumor assessment will be considered evaluable for anti-tumor efficacy using standard RECIST 1.1 criteria.

- PK analysis set.

The PK concentration population is defined as all treated patients who have at least 1 concentration of either of the study drugs.

The PK parameter analysis population is defined as all treated patients who have at least 1 of the PK parameters of interest of any of the study drugs.

- Biomarker analysis set.

The biomarker analysis set is defined as all treated patients who have at least one screening biomarker assessment, and have received at least one dose of any study drug. Analysis sets will be defined separately for blood-based and tumor tissue-based biomarkers.

If mutational profiling is performed on samples derived from the biomarker analysis set, the analysis may be limited to screening samples only.

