##### **9.4.1. Analysis of Efficacy Endpoints (Dose Expansion Phase Cohort)**

Objective response rate (ORR) is defined as the proportion of patients with a confirmed complete response (CR) or confirmed partial response (PR) according to RECIST version 1.1 definitions, relative to the response evaluable population. Confirmed responses are those that persist on repeat tumor assessments for at least 4 weeks after initial documentation or response. Otherwise, the patient will be counted as a non-responder in the assessment of ORR.

Time to Response (TTR) is defined as the time from first dose of study treatment to the first documentation of objective tumor response (CR or PR) that is subsequently confirmed.

Duration of Response (DR) is defined as the time from the first documentation of objective tumor response (CR or PR) that is subsequently confirmed to the first documentation of objective tumor progression or to death due to any cause, whichever occurs first.

Progression Free Survival (PFS) is defined as the time from the first dose of study treatment to the first progression of disease (PD) or death for any reason in the absence of documented PD. PFS will be summarized in the response evaluable population. PFS data will be censored on the date of the last tumor assessment on study for patients who do not have objective tumor progression and who do not die within 28 days of last dose. Patients lacking an evaluation of tumor response after enrollment will have their PFS time censored on the date of first dose with a duration of 1 day. Patients who are treated and removed from study

prior to on-study tumor assessment because of disease progression will be considered evaluable for efficacy and counted as an event at the time of progression. Additionally, patients who start a new anti-cancer therapy prior to documented PD will be censored at the date of the last tumor assessment prior to the start of the new therapy.

Overall Survival (OS) is defined as the time from the first dose of study treatment to the date of death due to any cause. OS will be summarized in the response evaluable population. For patients still alive at the time of the analysis, the OS time will be censored on the last date they were known to be alive. Patients lacking data beyond the day of first dose of study treatment will have their survival times censored at 1 day.

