6. ENDPOINTS AND COVARIATES

6.1. Efficacy Endpoints

Assessment of response will be made using RECIST version 1.1. All response statuses will be derived from lesion measurement data recorded on the electronic case report forms as provided by the investigator. .

Tumor assessments will include all known or suspected disease sites. Imaging may include chest, abdomen and pelvis CT or MRI scans; brain CT or MRI scan for patients with known or suspected brain metastases; bone scan for patients with known or suspected bone metastases.

The same imaging technique used to characterize each identified and reported lesion at baseline will be employed in the following tumor assessments.

Antitumor activity will be assessed through radiological tumor assessments conducted at baseline (screening), at 12 weeks, and every 6 weeks thereafter. In addition, radiological tumor assessments will also be conducted whenever disease progression is suspected (e.g. symptomatic deterioration) and at the time of withdrawal from the treatment (if not done in the previous 6 weeks).

- **Objective Response Rate (ORR)** is defined as the percent of patients with confirmed complete response (CR) or confirmed partial response (PR) according to the RECIST 1.1, relative to the response evaluable population. Confirmed responses are those that persist on repeat imaging study at least 4 weeks after initial documentation of response. Patients who do not have on-study radiographic tumor re-evaluation or who die, progress, or drop out for any reason prior to reaching a CR or PR will be counted as non-responders in the assessment of ORR. A patient who initially meets the criteria for a PR and then subsequently becomes a confirmed CR will be assigned a best response of CR.
- **Progression Free Survival (PFS)** is defined as the time from the date of first dose of MK-3475 (C1D1) to the date of the first documentation of objective tumor progression or death on-study due to any cause, whichever occurs first. If tumor progression data include more than 1 date, the first date will be used. PFS (in months) will be calculated as (first event date – first dose date +1)/30.44.

Patients lacking an evaluation of tumor response after the date of the first dose of MK-3475 (C1D1) will have their event time censored on the date of the first dose unless death occurs prior to 18 weeks (in which case the death is an event).

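### SAP 5.3 requires a dose of both drugs, so lead-in patients who never receive MK-3475 leave the efficacy analyses in which the protocol keeps them

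*SAP*

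**What the plan says.** **Set membership.** SAP 5.3: "All patients who receive study treatment (at least one dose of axitinib and MK-3475) with an adequate baseline tumor assessment". Protocol 9.1: "All patients who receive study treatment with an adequate baseline tumor assessment will be considered evaluable for anti-tumor efficacy", with no condition about both drugs. SAP 5.1 defines the safety set by a dose of one drug or the other, so the wording of 5.3 has to be read as requiring both.

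**What counts as study treatment.** Footnote 21 (registration) of the protocol's Schedule of Activities: "Study treatment (either single agent axitinib for patients in Lead-in or axitinib in combination with MK-3475 for all other patients".

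**Patients who stumble in the lead-in.** Under the DLT-evaluable set, Protocol 9.1 singles out anyone who, once the lead-in is over, cannot begin C1D1 at the dose level allotted to them. It says that such a patient "will not be evaluable for DLTs but will be evaluated for safety and efficacy". SAP 5.2 repeats the definition of that set but leaves this sentence out.

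**Time origin.** Protocol 9.4.1: "Progression Free Survival (PFS) is defined as the time from the first dose of study treatment to the first progression of disease (PD". In SAP 6.1, PFS "is defined as the time from the date of first dose of MK-3475 (C1D1", and TTR and OS start at the same point. SAP Appendix 2 also opens the efficacy on-study period at the first MK-3475 dose, yet takes the tumor baseline before the first dose of any study drug, which is axitinib for lead-in patients.

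**Who is exposed.** All Dose Finding patients and at least 8 Expansion patients have the 7-day axitinib lead-in. SAP 8.3.2 analyses tumor response, PFS and OS in the response-evaluable set, pooling the Expansion cohort with Dose Finding patients treated at the MTD.

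**The concern.** The two documents give different efficacy populations, and the difference is decided after treatment has started. A patient who takes axitinib in the lead-in and then progresses, dies or stops for toxicity before MK-3475 meets the protocol definition and fails the SAP one. That patient leaves the ORR denominator and contributes neither time nor an event to PFS or OS. The protocol's rule that a patient removed before an on-study scan "because of disease progression will be considered evaluable for efficacy and counted as an event at the time of progression" cannot operate for someone with no C1D1.

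An exclusion that depends on what happens on treatment is not neutral. Those most likely to miss MK-3475 include early failures, so the estimates describe patients who got through the lead-in rather than patients who were treated. The baseline rule adds an asymmetry: shrinkage during the lead-in counts toward response for those who continue, while those who fail in the lead-in are not counted.

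**Working it through.** **1. The plan's own figure.** SAP 8.1.3 and Protocol 9.3 bound the standard error of a proportion by 1/(2√n). With n = 40, 1/(2√40) = 0.0791, which reproduces the stated limit of 0.08. The choice of set does not alter that calculation. If one of exactly 40 Expansion patients left the set, the bound would be 1/(2√39) = 0.0801.

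**2. How many patients have the lead-in.** From the planned numbers: about 10 Dose Finding patients at the MTD plus 8 Expansion patients = 18, out of 10 + 40 = 50 pooled (36%). In Expansion alone it is at least 8 of 40 (20%).

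**3. Chance that anyone is excluded.** No document gives the proportion who never reach MK-3475. Assuming 5% to 10%, which is only an assumption:
- expected exclusions: 18 × 0.05 = 0.9 to 18 × 0.10 = 1.8;
- probability of at least one: 1 − 0.95^18 = 0.60 to 1 − 0.90^18 = 0.85.

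**4. Effect on ORR.** Take 50 patients under the protocol definition and let k of them be lead-in non-responders who never receive MK-3475. The protocol ORR is x/50 and the SAP ORR is x/(50 − k). The responder counts x are illustrative.

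| Responders x | Protocol set | SAP set, k = 1 | SAP set, k = 2 |
|---|---|---|---|
| 16 | 16/50 = 32.0% | 16/49 = 32.7% | 16/48 = 33.3% |
| 25 | 25/50 = 50.0% | 25/49 = 51.0% | 25/48 = 52.1% |

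The shift is 0.7 to 1.0 points for one patient and 1.3 to 2.1 for two. The exact 95% interval for 16/50 is 19.5% to 46.7%, and for 16/48 it is 20.4% to 48.4%.

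SAP 4.2 plans up to 40 response-evaluable Expansion patients, so excluded patients might instead be additional to the 50. The comparison is then 25/50 = 50.0% against 25/51 = 49.0% or 25/52 = 48.1%, a gap of similar size.

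**5. Time origin.** For a lead-in patient who goes on to MK-3475, starting at C1D1 rather than at first axitinib shortens PFS and OS by a nominal 7/30.44 = 0.23 months. For a patient who never receives MK-3475, the SAP origin does not exist. It is the both-drugs condition that removes patients; the choice of origin alone would remove nobody from ORR.

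**The case against.** **The SAP is allowed to differ.** Section 9 of the protocol lets the SAP modify its plans and asks for an amendment only for major changes to the primary endpoint or its analysis. Efficacy is secondary, SAP 4.1 stresses estimation over testing, and the objective is the activity of the combination. This stands: there is no procedural breach, and a both-drugs analysis from C1D1 answers a legitimate question. It does not make the exclusion unbiased, and the SAP gives no reason for it.

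**The affected group is narrow.** The protocol sentence concerns inability to start at the assigned dose level. A patient who starts the combination at another level has received both drugs and stays in the SAP set. For patients who do receive MK-3475, SAP 6.1 counts progression, death or dropout before response as non-response, and a death before 18 weeks without a scan as a PFS event. This also stands: only patients who never receive MK-3475 are lost.

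**They remain visible elsewhere.** They appear in the safety set, disposition, the lead-in adverse event summaries and the death listings. True, but none of these puts them back in ORR, PFS or OS.

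**Stronger readings a reader might infer.**
- That the exclusion can only favour every endpoint. Patients can also miss MK-3475 through withdrawal or loss to follow-up, and one who stopped for toxicity may survive long. The 0.23-month shift works the other way for those retained.
- That C1D1 gives pooled patients different origins. Under the SAP every patient starts at the first MK-3475 dose. It is the protocol origin that precedes the combination by about 7 days for lead-in patients and coincides with it for the rest.
- That the SAP's list of amendments concealed the change. The list compares SAP versions, not SAP with protocol, and the previous version is not available, so nothing can be concluded.

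**Conclusion.** The point holds for set membership. SAP 5.3 is narrower than Protocol 9.1, and it excludes from ORR, PFS and OS those lead-in patients who never receive MK-3475. The exclusion tends to raise ORR and probably flatters PFS and OS, without certainty for the last two.

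The size is small: about 0.7 to 2.1 ORR points for one or two such patients in a pooled set of 50, well inside the width of the confidence interval. That rests on assumed responder counts, on the excluded patients being non-responders, and on an unknown number of exclusions, which could be zero. The C1D1 origin is a defensible choice and not an error in itself; it matters here only because patients without a C1D1 need some origin once they are restored. The change is still worth making, because it removes an avoidable post-treatment exclusion and settles a direct disagreement between the documents.

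**What to change.** - In SAP 5.3, restore the protocol definition for ORR, PFS and OS: at least one dose of either study drug, with an adequate baseline tumor assessment.
- For that set, measure PFS and OS from the first dose of any study treatment, as in Protocol 9.4.1, and bring the SAP 6.1 censoring text and the Appendix 2 on-study period into line. State that progression or death before MK-3475 is an event.
- Report the number of patients who received axitinib but never MK-3475, with reasons.
- Keep the both-drugs set measured from C1D1 as a labelled secondary or sensitivity analysis.

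The cost is SAP wording and one additional set of efficacy tables. The listed endpoints need no new type of data. The downside is that the estimates may be slightly less favourable.
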